12.4.6 Response Review

It is strongly recommended that all responses be reviewed by an expert(s) independent of the study at the study’s completion.

13.0 DATA AND SAFETY MONITORING

In compliance with the Washington University Institutional Data and Safety Monitoring Plan, the Data and Safety Monitoring Committee (DSMC) will meet to review toxicity data at least every 6 months following the activation of the first secondary site. The report will be prepared by the statistician with assistance from the study team and will be submitted to the Quality Assurance and Safety Monitoring Committee (QASMC). This report will include:

- HRPO protocol number, protocol title, Principal Investigator name, data coordinator name, regulatory coordinator name, and statistician
- Date of initial HRPO approval, date of most recent consent HRPO approval/revision, date of HRPO expiration, date of most recent QA audit, study status, and phase of study
- History of study including summary of substantive amendments; summary of accrual suspensions including start/stop dates and reason; and summary of protocol exceptions, error, or breach of confidentiality including start/stop dates and reason
- Study-wide target accrual and study-wide actual accrual including numbers from participating sites
- Protocol activation date at each participating site
- Average rate of accrual observed in year 1, year 2, and subsequent years at each participating site
- Expected accrual end date and accrual by site
- Objectives of protocol with supporting data and list the number of participants who have met each objective
- Measures of efficacy
- Early stopping rules with supporting data and list the number of participants who have met the early stopping rules
- Summary of toxicities at all participating sites
- Abstract submissions/publications
- Summary of any recent literature that may affect the safety or ethics of the study

Until such a time as the first secondary site activates this protocol, a semi-annual DSM report to be prepared by the study team will be submitted to the QASM Committee beginning 6 months after study activation at Washington University.

The study principal investigator and Research Patient Coordinator will monitor for serious toxicities on an ongoing basis. Once the principal investigator or Research Patient Coordinator becomes aware of an adverse event, the AE will be reported to the HRPO and QASMC according to institutional guidelines.

A DSMC will consist of no fewer than 3 members including 2 clinical investigators and a biostatistician. Like investigators, DSMC members are subject to the Washington University School of Medicine policies regarding standards of conduct. Individuals invited to serve on the DSMC will disclose any potential conflicts of interest to the trial principal investigator and/or appropriate university officials, in accordance with institution policies. Potential conflicts that develop during a trial or a member's tenure on a DSMC must also be disclosed.

Refer to the Washington University Quality Assurance and Data Safety Monitoring Committee Policies and Procedures for full details on the responsibilities of the DSMC at http://www.siteman.wustl.edu/uploadedFiles/Research_Programs/Clinical_Research_Resources/Protocol_Review_and_Monitoring_Committee/QASMCQualityAssurance.pdf

14.0 AUDITING

Since Washington University is the coordinating center, each site will be audited annually by Siteman Cancer Center personnel (QASMC) unless the outside institution has an auditing mechanism in place and can provide a report. The outside sites will be asked to send copies of all audit materials, including source documentation. The audit notification will be sent to the Washington University Research Patient Coordinator, who will obtain the audit materials from the participating institution.

Notification of an upcoming audit will be sent to the research team one month ahead of the audit. Once accrual numbers are confirmed, and approximately 30 days prior to the audit, a list of the cases selected for review (up to 10 for each site) will be sent to the research team. However, if during the audit the need arises to review cases not initially selected, the research team will be asked to provide the additional charts within two working days.

Additional details regarding the Auditing Policies and procedures can be found at http://www.siteman.wustl.edu/uploadedFiles/Research_Programs/Clinical_Research_Resources/Protocol_Review_and_Monitoring_Committee/QASMCQualityAssurance.pdf

15.0 STATISTICAL CONSIDERATIONS

15.1 Sample Size

This is a single arm phase II trial. A single-stage design requires a total of 56 eligible patients to be enrolled in order to provide 81.64% power to test the desired 16 week clinical benefit rate (CBR) > 35% against an unfavorable CBR < 20% based on the exact binomial method at 5% significance level (actual significance level = 4.32%). Clinical benefit rate is defined as CBR = CR + PR + SD lasting \geq 16 weeks. If 17 or more patients benefit at the end of the trial, the treatment regimen yields a higher clinical benefit rate and warrants further investigation.

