15.2 Statistical Analysis

Clinical benefit rate will be calculated with 95% confidence interval (CI) based on the Wilson score method and compared to the pre-specified unfavorable CBR of 20% based on one-sided exact binomial test. The serum levels of sVEGFR2 and PIGF at each time point will be plotted and Pearson or Spearman's correlation coefficient will be calculated to explore their relationship. PFS and OS in the overall cohort of patients and by dichotomized sVEGFR2, PIGF and their combinations at each time point will be

analyzed and plotted by the Kaplan-Meier method with 95% CI. PFS and OS probabilities, overall and by group will be reported with 95% CI at desired time point. Cox proportional hazard model will be used to report resulting hazard ratio and Wald test P-values on sVEGFR2 and PIGF in continuous format.

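### Section 15.1 states 81.64% power, but the design it describes (n = 56, success at 17 or more, 20% vs 35%, exact binomial) has 80.64%; sample size and threshold stand

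*Combined protocol and SAP*

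**What the plan says.** Section 15.1 opens with "This is a single arm phase II trial" and gives the size and power: "A single-stage design requires a total of 56 eligible patients to be enrolled in order to provide 81.64% power". The rates are a "clinical benefit rate (CBR) > 35% against an unfavorable CBR < 20"%. The method is "based on the exact binomial method at 5% significance level (actual significance level = 4.32"%). The decision rule begins "If 17 or more patients benefit at the end of the trial"; in that case the regimen is taken to warrant further investigation.

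Section 15.2 confirms that the test is one-sided: the rate is to be "compared to the pre-specified unfavorable CBR of 20% based on one-sided exact binomial test". It also plans an interval: "Clinical benefit rate will be calculated with 95% confidence interval (CI) based on the Wilson score method". Neither section gives a second power figure.

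**The concern.** Sections 15.1 and 15.2 together fix every input of an exact binomial calculation, and the results are printed to two decimals. Significance level and power should then both follow from the one rule. The significance level does. The power does not.

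Readers take the operating characteristics of the trial from this sentence. It suggests a margin of 1.64 points over the usual 80%, when the true margin is 0.64 point. Anyone who recomputes the design will find the mismatch and may wonder whether the sample size or the threshold is wrong as well.

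**Working it through.** **Inputs**

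- n = 56 eligible patients, success at r = 17 or more, one stage (section 15.1)
- p0 = 0.20 and p1 = 0.35 (section 15.1)
- exact binomial test (section 15.1), one-sided (section 15.2)

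**Formula.** With X the number of patients with clinical benefit, P(X ≥ r | n, p) = Σ C(n, k) p^k (1 − p)^(n − k), summed over k = r to n. Setting p = p0 gives the type I error, and p = p1 gives the power.

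**Step 1: the plan's significance level.** P(X ≥ 17 | 56, 0.20) = 0.04321, or 4.32%. This equals the stated actual level, so n, threshold, null rate and sidedness are all confirmed.

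**Step 2: the plan's power.** P(X ≥ 17 | 56, 0.35) = 0.80642, or 80.64%. The plan says 81.64%. The difference is 81.64 − 80.64 = 1.00 point. The type II error is 100 − 80.64 = 19.36%, not 100 − 81.64 = 18.36%.

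**Step 3: could another reading give 81.64%?**

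Other thresholds at n = 56:

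| Threshold | Type I error | Power at 35% |
|---|---|---|
| 16 | 7.95% | 87.58% |
| 17 | 4.32% | 80.64% |
| 18 | 2.19% | 71.85% |

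Other sample sizes, each with the smallest threshold that keeps the exact type I error at or below 5%:

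| n / threshold | Type I error | Power at 35% |
|---|---|---|
| 52 / 16 | 4.36% | 78.20% |
| 55 / 17 | 3.67% | 77.97% |
| 56 / 17 | 4.32% | 80.64% |
| 57 / 18 | 2.61% | 74.93% |
| 58 / 18 | 3.10% | 77.78% |
| 59 / 18 | 3.65% | 80.40% |
| 60 / 18 | 4.27% | 82.79% |

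For n = 40 to 59 the power never reaches 81.64%; the first design above it is 60/18. If the limit on type I error is dropped, no n from 20 to 120 with any threshold gives 81.64% at 35%.

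One-sided approximations at n = 56:

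| Method | Level 5% | Level 4.32% |
|---|---|---|
| Normal | 83.50% | 82.00% |
| Normal, continuity-corrected | 79.78% | 78.09% |
| Wald | 76.07% | 73.85% |
| Arcsine | 81.34% | 79.41% |

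The two-sided versions are all at or below about 76.1%. None equals 81.64%, and the plan names the exact method in any case.

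A different true rate: the 56/17 rule reaches 81.64% only if the true rate is 35.24%, which the plan does not state.

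**Step 4: does the design survive the correction?** Yes. In the search from n = 40 to 65, 56/17 is the smallest design with exact type I error at or below 5% and power of at least 80%. The corrected figure therefore supports the choice of 56.

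**Side check: the interval in section 15.2.** The test is one-sided at 5%, but a two-sided 95% interval corresponds to 2.5% on each side.

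| Patients with benefit | One-sided exact p | Wilson 95% lower limit |
|---|---|---|
| 16 | 0.0795 | 18.42% |
| 17 | 0.0432 | 19.90% |
| 18 | 0.0219 | 21.40% |

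At exactly 17/56 the interval (19.90% to 43.34%) includes 20% although the test rejects. At 16 both fail, and at 18 both succeed.

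**The case against.** The strongest reply is that nothing in the trial depends on the figure. Sample size, threshold, significance level and primary test are all correct, true power is above 80%, and a gap of one point would pass many tolerance checks. This stands as a statement about weight, and it is why the point is minor. It does not make 81.64% right: a tolerance suits approximate methods or incomplete inputs, whereas here the method is exact, every input is given, and the significance level in the same sentence agrees to the last printed digit.

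A second reply is that the digit may have been misread when the PDF was converted to text. There is no sign of this, but a look at the source file settles it.

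A third is that the loss of power with 55 eligible patients (77.97%) reflects the discreteness of exact designs and not the wrong figure. That is correct; the example shows only how thin the true margin is.

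Finally, the plan never uses the Wilson interval for the decision, and a two-sided 95% interval beside a one-sided 5% test is common practice. That is also correct, so the remark on section 15.2 is optional and is not counted as an error.

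**Conclusion.** The concern holds and is minor. The design in section 15.1 has exact power of 80.64%; the stated 81.64% is too high by 1.00 percentage point. The margin over 80% is 0.64 point instead of 1.64 points. The result needs no assumption beyond the plan's own inputs, and the agreement on 4.32% confirms that they were read as intended. The decimals are the same and the gap is one whole point, so a one-digit typing error is the likely cause, though that is an inference. This is one wrong number, not a design error: 56 patients and a threshold of 17 remain adequate.

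**What to change.** In section 15.1, check the digit against the source file and replace 81.64% with 80.64%. Keep n = 56, the threshold of 17 and the stated 4.32%. The cost is one figure, and a stated power that looks 1.00 point less favourable.

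Optionally, add a sentence to section 15.2 saying that the one-sided exact test governs the conclusion if the 95% interval appears to disagree, which can happen only at 17/56. Alternatively, report a two-sided 90% interval as well; at 17/56 this is 21.35% to 41.17% by Wilson or 20.35% to 41.99% by Clopper-Pearson, and both exclude 20%. Of the two, Clopper-Pearson follows the exact test more closely: at 16/56, where the test does not reject (p = 0.0795), its lower limit must also lie below 20%. The Wilson 90% lower limit there is 19.81%, so it agrees as well.

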15.2 Statistical Analysis

Clinical benefit rate will be calculated with 95% confidence interval (CI) based on the Wilson score method and compared to the pre-specified unfavorable CBR of 20% based on one-sided exact binomial test. The serum levels of sVEGFR2 and PIGF at each time point will be plotted and Pearson or Spearman's correlation coefficient will be calculated to explore their relationship. PFS and OS in the overall cohort of patients and by dichotomized sVEGFR2, PIGF and their combinations at each time point will be

analyzed and plotted by the Kaplan-Meier method with 95% CI. PFS and OS probabilities, overall and by group will be reported with 95% CI at desired time point. Cox proportional hazard model will be used to report resulting hazard ratio and Wald test P-values on sVEGFR2 and PIGF in continuous format.

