5.4 Duration of Therapy

If at any time the constraints of this protocol are considered to be detrimental to the patient's health and/or the patient no longer wishes to continue protocol therapy, the protocol therapy should be discontinued and the reason(s) for discontinuation documented in the case report forms.

In the absence of treatment delays due to adverse events, treatment may continue indefinitely until one of the following criteria applies:

- Documented and confirmed disease progression
- Death
- Adverse event(s) that, in the judgment of the investigator, may cause severe or permanent harm or which rule out continuation of study drug
- General or specific changes in the patient's condition render the patient unacceptable for further treatment in the judgment of the investigator
- Suspected pregnancy
- Serious non-compliance with the study protocol
- Lost to follow-up
- Patient withdraws consent
- Investigator removes the patient from study
- The Siteman Cancer Center decides to close the study

Patients who prematurely discontinue treatment for any reason other than withdrawal of consent will be followed as indicated in the study calendar.

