10.0 STUDY CALENDAR

Screening assessments must be performed no more than 14 days prior to start of study treatment, except scans which may take place up to 28 days prior to the start of treatment. After the start of study treatment, there is a ± 7 day window for all exams, scans, labs and procedures to be performed. Please note, there is also a ± 7 day window for treatment and for routine office visits.

	Screening	D1 of each cycle	C1D5	C1D8	C1D9	C1D15 and C2D15	End of every even-numbered cycle	EOT	F/U ¹	
Informed consent	X									
PE, H&P, PS	X	X						X		
VS	X	X		X				X		
CBC	X	X		X				X		
CMP	X	X		X				X		
LFTs ²	X	X ²		X ²		X ²		X		
Pregnancy test ³	X							X		
UPC	X	X ⁴						X		
TSH, FT4	X	X ⁵								
PT/PTT, INR	X							X		
ECG	X	X ⁶								
ECHO ¹⁰	X									
CT scan	X						X	X		
Pazopanib		X	-----					X ⁷		
FACT-G		X ⁸				X ⁸				
Blood for biomarkers		X ⁹								
Collect/review drug diary		X								
Toxicity assessment	X	X						X		

1. Every 3 months until death.

2. Monitor serum liver tests (total bilirubin, ALT/AST) before initiation of treatment with pazopanib and on C1D15, C2D1, C2D15, C3D1, C4D1, C5D1, and as clinically indicated (± 3 days). Periodic monitoring should continue after C5.

3. Women of childbearing potential only.

4. D1 of each cycle through C6, then D1 of every even-numbered cycle thereafter.

5. Monitor between every 8 to every 16 weeks.

6. C2D1, C4D1, C7D1, and then every 16 weeks (D1 of every 4th cycle) until EOT.

7. To be taken PO each day. Each cycle is 4 weeks long. See Section 5.1 for dosing instructions.

8. Baseline (prior to C1D1), C1D15, and D1 of every cycle thereafter.

9. Baseline (prior to C1D1), C2D1, C3D1, and C4D1.

10. Baseline (prior to C1D1) and periodic reassessment as needed and/or as indicated. Consistent diagnostic imaging should be used throughout study.

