12.0 MEASUREMENT OF EFFECT

12.1 Antitumor Effect – Solid Tumors

For the purposes of this study, patients should be re-evaluated for response 8 weeks after initiation of pazopanib and then every 8 weeks thereafter. In addition to a baseline scan, confirmatory scans should also be obtained not less than 8 weeks following initial documentation of objective response.

Response and progression will be evaluated in this study using the new international criteria proposed by the revised Response Evaluation Criteria in Solid Tumors (RECIST) guideline (version 1.1) [Eur J Ca 45:228-247, 2009]. Changes in the largest

diameter (unidimensional measurement) of the tumor lesions and the shortest diameter in the case of malignant lymph nodes are used in the RECIST criteria.

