12.4.5 Progression-Free Survival

Progression-free survival is defined as the duration of time from start of treatment to time of progression or death, whichever occurs first.

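### Kaplan-Meier PFS by C4D1 (and partly C3D1) marker group has no landmark, so its probabilities are conditional on reaching the draw and are not comparable with PFS from treatment start

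*Combined protocol and SAP*

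**What the plan says.** - **Analysis (Section 15.2).** Kaplan-Meier PFS and OS are planned for the overall cohort "and by dichotomized sVEGFR2, PIGF and their combinations at each time point will be" analyzed and plotted. The section adds that "PFS and OS probabilities, overall and by group will be reported with 95% CI at desired time point". A Cox model takes each marker as a continuous variable. No landmark, delayed entry, time-dependent covariate or rule for patients who progress before a draw is given.
- **Time origin (Section 12.4.5).** "Progression-free survival is defined as the duration of time from start of treatment to time of progression or death, whichever occurs first". No origin is stated for OS.
- **Draws (Section 10.0, footnote 9).** "Baseline (prior to C1D1), C2D1, C3D1, and C4D1". These are on-treatment visits; the calendar has no marker sample at end of treatment or in follow-up. With 28-day cycles (Section 5.1) the draws fall at weeks 0, 4, 8 and 12.
- **Scans (Section 12.1).** "patients should be re-evaluated for response 8 weeks after initiation of pazopanib and then every 8 weeks thereafter". Section 10.0 allows a ± 7 "day window for all exams, scans, labs and procedures to be performed".
- **End of treatment (Section 5.4).** One criterion is "Documented and confirmed disease progression". The documents give no general interval for confirming progression.

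**The concern.** A patient has a C4D1 value only if still on treatment at about week 12. Even at the edges of the two windows, an on-schedule first scan is done by about week 9 and C4D1 is drawn no earlier than about week 11. The scan therefore comes first, and most patients who fail it can be expected to have left treatment before the draw. Their PFS events count in the overall curve and are missing from every C4D1 curve.

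Timed from treatment start, a C4D1 curve stays close to 100% until after week 8 by construction. It estimates roughly S(t)/S(8), where S is PFS in the whole cohort, and not S(t). At C3D1 the scan and the draw coincide within their windows, so the effect is partial. At C2D1 no scan precedes the draw, and only early deaths or other early stops act.

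Section 1.4 wants to confirm a week-12 association and look for an earlier one, so readers will compare curves across weeks 0, 4, 8 and 12. Later groups would look better than baseline groups and the overall cohort through selection alone.

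A second problem arises if a week-8 progressor is still on drug pending confirmation and is sampled at C4D1. That marker is measured after the PFS event it is meant to explain, and the plan has no rule for this.

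**Working it through.** The documents state no figure for the marker analysis, so there is none to reproduce. The sizes below are illustrations for a marker with no effect.

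**Inputs**
- First scan at week 8, then every 8 weeks (Section 12.1); C3D1 at week 8 and C4D1 at week 12.
- Scenario 1: median PFS 4.6 months (Section 1.2). Those patients were previously treated, so this is an assumption here. 4.6 months = 20.0 weeks. The 26-week reading is also an assumption; the plan names no time point.
- Scenario 2: the design rates of Section 15.1 ("desired 16 week clinical benefit rate (CBR) > 35% against an unfavorable CBR < 20", in percent), treating 16-week clinical benefit as being progression-free after the week-16 scan.
- Constant hazard, and progression dated at the scan.

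**Step 1: no week-8 progressor sampled at C4D1.** The group shows S(t)/S(8).
- Scenario 1: S(8) = 0.5^(8/20) = 0.758 and S(24) = 0.5^(24/20) = 0.435. Week-26 PFS is S(24) = 43.5% overall and 0.435/0.758 = 57% in C4D1 groups. A 3-month median gives 28% against 43%; a 6-month median gives 53% against 65%.
- Scenario 2: S(8) = √p. For p = 0.35, 0.35/0.592 = 59%. For p = 0.20, 0.20/0.447 = 45%. Weibull shapes from 1.5 to 0.75 give 51% to 65% and 35% to 52%.

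**Step 2: a fraction f of week-8 progressors is sampled.** The group shows S(t)/[S(8) + f(1 − S(8))].

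| f | 43.5% appears as | 35% appears as | 20% appears as |
|---|---|---|---|
| 0 | 57% | 59% | 45% |
| 0.10 | 56% | 55% | 40% |
| 0.25 | 53% | 50% | 34% |
| 0.50 | 50% | 44% | 28% |
| 0.75 | 46% | 39% | 23% |
| 1 | 43.5% | 35% | 20% |

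**Step 3: C3D1 and C2D1.** Simulating scenario 1 with scan and draw each uniform within 7 days of schedule gives about 49% at C3D1, and no excess at C2D1. If 0%, 50% or 100% of week-8 progressions are found before the C3D1 draw, scenario 2 with p = 0.35 gives 35%, 44% or 59%. If 20% of events are deaths at any time (and half of week-8 progressions precede the C3D1 draw), simulated groups show 37% at C2D1, 46–47% at C3D1 and 62% at C4D1, against 34.9% overall.

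**Step 4: numbers and precision.** Expected at C4D1 with f = 0: 56 × 0.758 = 42, or about 34 if 20% of those stop for other reasons; 56 × 0.592 = 33; 56 × 0.447 = 25. With a median split and no censoring, the group's 95% CI (log-log) still contains the overall value in about 86% of trials for 21 patients in scenario 1. In scenario 2 it does so in about 70% (16 patients, p = 0.35) and about 53% (12 patients, p = 0.20).

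**Step 5: Cox model.** Among simulated patients whose events all fall after week 12, the coefficient is 0.3032 from either time origin. This does not test the case where a progressor is sampled after the event.

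**The case against.** The strongest reply is that this is a labelling matter. A C4D1 probability is valid as a figure conditional on reaching C4D1. If no week-8 progressor is sampled, a landmark gives the same number at the same calendar date (57% in scenario 1). Section 15.2 plans no test of a marker group against the overall cohort, and Secondary Objective 4 asks only for correlation. Much of this stands, and it is why the point is minor. It does not remove the point: Section 12.4.5 fixes the clock at treatment start, Section 15.2 commits to reporting both sets of probabilities, and nothing in the plan marks the later ones as conditional.

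It is also fair that the strength of the selection is undocumented. Section 5.4 requires confirmed progression, Section 12.4.2 leaves confirmation of non-target progression to a later time, and nothing limits f. At f = 1 the excess is zero. But then every week-8 progressor contributes a marker measured after the event, so a landmark is still needed for a different reason.

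A reader might infer that the landmark never changes the C4D1 number. That holds only at f = 0. At f = 0.50 in scenario 1, a progression-free landmark moves 49.5% to 57.4%, further from the overall 43.5%, because it answers a different and properly labelled question.

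A reader might also infer that high-versus-low contrasts and hazard ratios are inflated by the missing landmark, or that they are wholly safe. The documents support neither. With no progressor sampled, all patients at a time point pass the same condition and the hazard ratio does not depend on the origin. With progressors sampled, contrasts and Cox estimates are affected, in a direction and size the documents do not settle.

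**Conclusion.** The point holds as a minor one, in a secondary correlative analysis. Following the plan as written, C4D1 and partly C3D1 group probabilities are conditional on reaching the draw. They exceed PFS from treatment start for an uninformative marker whenever some week-8 progressors go unsampled. The direction follows from the schedule. The size rests on constant hazard, a borrowed median or the design rates, and an unknown f: at C4D1 it runs from no excess (f = 1) to about 14 points in scenario 1 (57.4 − 43.5) and about 24 to 25 points in scenario 2 (59.2 − 35; 44.7 − 20) at f = 0. An informative marker could still put its poor-prognosis group below the overall curve.

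OS by group is exposed to a similar selection, which is not quantified here. Baseline-marker analyses, overall PFS and OS, and the primary clinical benefit test are unaffected. A reader might infer that the trial's main conclusion is at risk; the documents do not support that.

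**What to change.** Amend Section 15.2 for markers drawn at C2D1, C3D1 and C4D1:

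- Use a landmark analysis for both Kaplan-Meier and Cox, with time zero at the sampling visit.
- For PFS, include only sampled patients who are alive and progression-free at that date. For OS, include all sampled patients alive.
- Report results as conditional on reaching the landmark (for example, PFS 14 weeks after C4D1) and not as comparable with PFS from treatment start.
- At C3D1, state whether the week-8 scan preceded the draw, or set the landmark after that scan. Otherwise the group mixes patients who have and have not been scanned.
- Keep treatment start as time zero for baseline markers and overall PFS, and state the OS origin for the overall cohort.

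Delayed entry alone is not enough. In the scenario 1 simulation it brings C3D1 from 49% to 44%, but C4D1 stays at 57% because nobody is at risk before the draw.

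The cost is a few sentences and a small programming change, with no new data. The downside is fewer patients at later landmarks: about 25 to 42 of 56 at C4D1 under the assumptions shown.
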